## **21.7 Pharmacodynamic Analysis**

### **21.7.1 Central histopathologic review and tissue requirements**

At least 20 unstained FFPE slides from a representative block of tumor tissue (0.5 cm diameter) should be submitted on all participants in the study. One slide will be H&E stained at the central site to confirm diagnosis and determine eligibility for further study. The remaining slides will be utilized for MGMT methylation assessment, biomarker analysis, and correlation of treatment effect with genotype and phenotype.

### **21.7.2 Tissue Evaluation**

The rationale for evaluation of tumor tissue is two-fold: 1) to analyze prognostic molecular factors to be able to compare the data vs. historical control data, and 2) to conduct exploratory evaluation of biomarkers of Fms inhibition, as well as correlation of clinical outcomes with response and tumor parameters. Because of the importance of this tumor tissue evaluation, surgical samples are required, and biopsy-only samples are not allowed.

Planned biomarkers are listed in [Attachment 1](#). The staining patterns will be semi-quantitatively and manually scored and correlated with other measures for number of TAMs and their morphology and location within the tumor.

No formal statistical analysis of PD endpoints will be performed. PD data from each assay will be listed, and possible relationships between clinical response and PD variables will be explored. Any biological activity will be described.

### 21.7.3 Serum biomarker analysis

Serum biomarkers will also be assayed at a central laboratory. Please consult the laboratory manual for shipping and handling instructions.

## 22.0 PRECAUTIONS

Although major adverse events are not anticipated, the investigator must proceed with utmost caution. Equipment, supplies, and properly skilled medical personnel must be immediately available for emergency use in the event of an unexpected reaction. Patients must be carefully selected and closely monitored.

For a complete description of preclinical and clinical studies of PLX3397, please refer to the PLX3397 Investigator's Brochure.

## 23.0 ADVERSE EVENTS

For safety information on PLX3397, refer to the most recent version of the Investigator's Brochure.

### 23.1 Definitions

An **adverse event** (AE) is any untoward, undesired, or unplanned event in the form of signs, symptoms, disease, or laboratory or physiologic observations occurring in a person given a study drug in a clinical study. The event does not need to be causally related to the study drug. An AE includes, but is not limited to, the following:

- Any clinically significant worsening of a preexisting condition.
- An AE occurring from overdose (i.e., a dose higher than that indicated in the protocol) of a study drug, whether accidental or intentional.
- An AE occurring from abuse (e.g., use for nonclinical reasons) of a study drug.
- An AE that has been associated with the discontinuation of the use of a study drug.

Any treatment-emergent abnormal laboratory result which is clinically significant, i.e., meeting one or more of the following conditions, should be recorded as a single diagnosis on the adverse event page in the eCRF:

- Accompanied by clinical symptoms
- Leading to a change in study medication (e.g., dose modification, interruption or permanent discontinuation)

- Requiring a change in concomitant therapy (e.g., addition of, interruption of, discontinuation of, or any other change in a concomitant medication, therapy or treatment)

A **serious adverse event** is an AE that:

- Results in death (NOTE: death is an outcome, not an event)
- Is life-threatening.
- Requires inpatient hospitalization or prolongation of an existing hospitalization.
- Results in a persistent or significant disability or incapacity.
- Results in a congenital anomaly or birth defect.
- Additionally, important medical events that may not result in death, be life-threatening, or require hospitalization may be considered SAEs when, based on appropriate medical judgment, they may jeopardize the patient and may require medical or surgical intervention to prevent one of the outcomes listed in this definition. Examples of such events include allergic bronchospasm requiring intensive treatment in an emergency room or at home, blood dyscrasias or convulsions that do not result in hospitalization, or development of drug dependency or drug abuse.

**Clear progression of neoplasia should not be reported as an adverse event or serious adverse event.** Findings that are clearly consistent with the expected progression of the underlying cancer should not be reported as an adverse event, and hospitalizations due to the progression of cancer do not necessarily qualify for a serious adverse event. Sudden and unexplained death should be reported as an SAE. If there is any uncertainty about a finding being due solely to progression of neoplasia, the finding should be reported as an adverse event or serious adverse event as appropriate.

**Life-threatening** refers to immediate risk of death as the event occurred per the reporter. A life-threatening experience does not include an experience, had it occurred in a more severe form, which might have caused death, but as it actually occurred, did not create an immediate risk of death. For example, hepatitis that resolved without evidence of hepatic failure would not be considered life-threatening, even though hepatitis of a more severe nature can be fatal. Similarly, an allergic reaction resulting in angioedema of the face would not be life-threatening, even though angioedema of the larynx, allergic bronchospasm, or anaphylaxis can be fatal.

**Hospitalization** is official admission to a hospital. Hospitalization or prolongation of a hospitalization constitutes criteria for an AE to be serious; however, it is not in itself considered a serious adverse event (SAE). In absence of an AE, a hospitalization or prolongation of a hospitalization should not be reported as an SAE. This is the case in the following situations:

- The hospitalization or prolongation of hospitalization is needed for a procedure required by the protocol. Day or night survey visits for biopsy or surgery required by the protocol are not considered serious.

- The hospitalization or prolongation of hospitalization is part of a routine procedure followed by the center (e.g., stent removal after surgery). This should be recorded in the study file.
- Hospitalization for survey visits or annual physicals falls in the same category.

In addition, hospitalizations planned before the start of the study, for a preexisting condition that has not worsened, do not constitute an SAE. An emergency room visit is not considered a hospitalization unless it results in a hospitalization.

**Disability** is defined as a substantial disruption in a person's ability to conduct normal life functions.

If there is any doubt about whether the information constitutes an SAE, the information is treated as an SAE.

Relatedness to study medication will be graded as either "probably", "possibly", or "not related", as follows:

**Probably** – The adverse event

- Follows a reasonable temporal sequence from drug administration
- Abates upon discontinuation of the drug
- Cannot be reasonably explained by the known characteristics of the patient's clinical state

**Possibly** – The adverse event

- Follows a reasonable temporal sequence from drug administration
- Could have been produced by the patient's clinical state or by other modes of therapy administered to the patient

**Not Related** – The adverse event

- Does not follow a reasonable sequence from drug administration
- Is readily explained by the patient's clinical state or by other modes of therapy administered to the patient

A **protocol-related adverse event** is an AE occurring during a clinical study that is not related to the study drug, but is considered by the investigator or the medical monitor (or designee) to be related to the research conditions, i.e., related to the fact that a patient is participating in the study. For example, a protocol-related AE may be an untoward event occurring during a washout period or an event related to a medical procedure required by the protocol.

Other **Reportable Information**: certain information, although not considered an SAE, must be recorded, reported, and followed up as indicated for an SAE. This includes:

- A case involving a pregnancy exposure to a study drug, unless the product is indicated for use during pregnancy e.g., prenatal vitamins. Information about use in pregnancy encompasses the entire course of pregnancy and delivery and perinatal and neonatal outcomes, even if there were no abnormal findings. If a pregnancy is confirmed, study drug must be discontinued immediately. All reports of pregnancy must be followed for information about the course of the pregnancy and delivery, as well as the condition of the newborn. When the newborn is healthy, additional follow-up is not needed. Pregnancies occurring up to 6 months after completion of the study treatment must also be reported to the investigator.
- Overdose (e.g., a dose higher than that indicated in the protocol) with or without an AE.
- Abuse (e.g., use for nonclinical reasons) with or without an AE.
- Inadvertent or accidental exposure with or without an AE.
- Device malfunction with or without an AE.

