### **11.0 SELECTION OF STUDY POPULATION**

All patients must participate in the consent process. During the consent process, the person obtaining consent must inform the patient of all elements of informed consent. No protocol-specific procedures, including screening procedures, are to be performed until the patient has signed and dated an institutional review board (IRB)/independent ethics committee (IEC)-approved informed consent form. The study begins with the signing and dating of the informed consent form. Patients must also meet the inclusion and exclusion criteria to be enrolled in the study.

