## 12.0 CONCOMITANT TREATMENT

Concomitant treatment is permitted if the medication is not expected to interfere with the evaluation of safety or efficacy of the study drug. During the study, if the use of any concomitant treatment becomes necessary (e.g., for treatment of an adverse event), the treatment must be recorded on the eCRF, including the reason for treatment, generic name of the drug, dosage, route, and date of administration.

Patients enrolling in studies with PLX3397 who are also receiving concomitant warfarin should have their anti-coagulation status carefully monitored, especially shortly after initiation of PLX3397, for the potential need to make adjustments in warfarin dosing. In particular, INR should be obtained just prior to initiation of PLX3397, within 1-2 weeks after initiation, and periodically thereafter. Dose adjustments of warfarin should be made as medically indicated.

Although PLX3397 does not appear to inhibit CYP drug-metabolizing enzymes to an important extent, caution is warranted when administering PLX3397 to subjects taking drugs that are highly dependent on CYP3A4 for metabolism and have a narrow therapeutic index. It is not known whether systemic exposure to these medications will demonstrate an increase while patients are receiving PLX3397.

Of the five major CYP isoforms, 3A4 (BFC) may be involved in Phase I metabolism of PLX3397, with possibly CYP1A2 playing a minor role. Until information regarding exposure-toxicity and exposure-response relationships are available with PLX3397, concomitant CYP3A4 inhibitors and inducers should be administered with caution, in the event they alter the systemic exposure to PLX3397 (see [Attachment 2](#) for a list of strong CYP3A4 inhibitors and inducers). In general, strong inhibitors or inducers of CYP3A4 should be avoided unless absolutely necessary. These include anticonvulsants (phenytoin, carbamazepine, phenobarbital), mycin antimicrobials, and antiretrovirals. Strong CYP 3A4 inducers or inhibitors should be discontinued at least 14 days prior to the initiation of dosing with PLX3397.

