### 13.2 Cycle 1 Day 1 (- 2 Days), [4 week cycle]

The C1D1 visit must occur any Monday through Friday  $\geq 3$  weeks and  $\leq 5$  weeks since surgery. At this visit, all patients will return to the clinic and undergo the following procedures:

1. Weight, vital signs, neurological exam plus symptom-directed physical examination.

2. Clinical laboratory evaluation (hematology and serum chemistry).
3. For Phase 1b dose escalation patients only: Pre-dose blood sample collection for PK.
4. Pre-dose blood sample collection for PD response biomarkers and CD14/16 mononuclear cell counts.
5. Karnofsky performance status assessment.
6. MDA Symptom Inventory.
7. Recording of concomitant medications.
8. Initiation of dosing with study drug either 7 days/week or 5 days/week (Monday through Friday).
9. AE Monitoring, beginning after first dose of study drug.

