## **18.0 SAFETY EVALUATION**

Routine safety and tolerability will be evaluated from the results of reported signs and symptoms, scheduled physical examinations, vital sign measurements, 12-lead ECGs (including QTcF intervals), and clinical laboratory test results.

More frequent safety evaluations may be performed if clinically indicated or at the discretion of the investigator. All AEs will be recorded from the time the patient receives the first dose of study drug up to 28 days after the last dose.

As this is an open label study, ongoing safety will be continuously and rigorously monitored by the Sponsor. Additionally, biweekly teleconferences are planned to review in detail the safety across all study sites.

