### **23.2 Recording and Reporting**

A patient's AE or SAE can occur from the time the patient receives the first dose of study drug up to 28 days after the last dose.

The investigator must follow-up on all drug-related AEs, SAEs, and other reportable information until the events have subsided, returned to baseline, the patient has initiated any other anticancer treatment, or in case of permanent impairment, until the condition stabilizes. Pregnancies and overdoses are not considered AEs but must be reported to the Sponsor.

All AE and SAEs must be recorded on source documents and collected in TEMPO. All AEs and SAEs for patients who are not screen failures will be recorded in the eCRFs.

AEs should be based on the signs or symptoms detected during the physical examination and on clinical evaluation of the patient. In addition to the information obtained from those sources, the patient should be asked the following nonspecific question: "How have you been feeling since your last visit?" Signs and symptoms should be recorded using standard medical terminology.

Any unanticipated risks to the patients must be reported promptly to the IRB/IEC.

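### Protocol-related AEs and SAEs, which the protocol itself defines, are not captured between consent and the first PLX3397 dose

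*Combined protocol and SAP*

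**What the plan says.** Three sections set the start of recording, and they agree. Section 18.0: "All AEs will be recorded from the time the patient receives the first dose of study drug". Section 23.2: an AE or SAE "can occur from the time the patient receives the first dose of study drug up to 28 days after the last dose". Section 13.2, last item: "AE Monitoring, beginning after first dose of study drug". AE monitoring is not among the screening procedures in Section 13.1, and the Screening column of both flow charts has no entry in the adverse event row. The general definition in Section 23.1 ties an AE to someone who has received study drug.

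The same Section 23.1 then defines a protocol-related AE as one that is unrelated to study drug but is judged by the investigator or medical monitor to stem from being in the study. As its example it says that such an event "may be an untoward event occurring during a washout period or an event related to a medical procedure required by the protocol".

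Section 11.0 places the start earlier than the first dose: "The study begins with the signing and dating of the informed consent form". Section 12.0 adds an instruction that acts before dosing: "Strong CYP 3A4 inducers or inhibitors should be discontinued at least 14 days prior to the initiation of dosing with PLX3397". The drugs it names include phenytoin, carbamazepine and phenobarbital. On screen failures, Section 23.2 says: "All AEs and SAEs for patients who are not screen failures will be recorded in the eCRFs".

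**The concern.** The protocol creates a category for harm that comes from taking part rather than from the drug, and illustrates it with washout and procedure events. Its recording window opens only after the pre-dose stage, where such events can also arise. Nothing in the plan collects an AE or SAE between consent and first dose.

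The period is not empty. Stopping an enzyme-inducing anticonvulsant at the protocol's instruction falls in it, in a population where Section 13.13.2 describes seizures as common. Section 23.1 lists convulsions that do not lead to hospitalization among its examples of important medical events that may count as SAEs. Such an event would be an SAE candidate one day after dosing and outside the reporting system one day before.

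The loss also depends on outcome. A patient whose event keeps them from being dosed is, under Section 11.3, a screen failure, and Section 23.2 leaves that group out of eCRF event recording. The most serious pre-dose events are therefore the ones most likely to be missing from SAE reporting.

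**Working it through.** No sample size, error rate or power figure is involved, and the plan states no figure to reproduce. The check is a comparison of the timelines and definitions.

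1. **Recording window.** It opens at the first dose on C1D1 and closes 28 days after the last dose (Sections 13.2, 18.0, 23.2).
2. **Time on study before the window.** The study begins at consent (Section 11.0). Screening is Day -21 to Day -1 (flow charts; Section 13.1). Up to 21 days on study therefore precede any AE or SAE capture.
3. **Position of the instructed withdrawal.** It should start no later than Day -14 (Section 12.0). All of its pre-dose days lie outside the window. C1D1 is 3 to 5 weeks after surgery (Section 13.2), so the latest start is 21 - 14 = 7 to 35 - 14 = 21 days after surgery.
4. **Uncaptured withdrawal days per patient.** Let consent be s days before C1D1 (s at most 21) and the drug be stopped w days before C1D1 (w at least 14). The on-study withdrawal days with no capture are min(s, w).
   - Consent at Day -21, stop at Day -14: min(21, 14) = 14 days, or 14/21 = 67% of screening.
   - Consent at Day -7, drug already stopped at Day -14: min(7, 14) = 7 days.
   - Drug continued under the Section 12.0 exception: 0 days.

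   The range is thus 0 to 21 days per patient on such a drug. It is not a fixed minimum of 14.
5. **Total exposure.** This is the sum of min(s, w) over patients who stop such a drug. The documents give neither the number of these patients nor an event rate, so the total cannot be computed.
6. **Definitions side by side.** Under the general AE definition, an undosed person cannot have an AE. Screen failures receive no study drug (Section 11.3), so they cannot have one either. The Section 23.2 sentence on screen failures is then either redundant or a sign that pre-dose events were meant to count. It does not settle the matter, but it shows that the sections were not aligned.
7. **Route for an SAE.** Section 23.3 sends SAE reports through a form in the eCRF, with fax as back-up. Neither route is opened for an event before first dose.
8. **What does capture something.** Medical history and concomitant medications are taken at Screening (Section 13.1). Section 11.3 requires a log of screen failures with the reason, tracked in the EDC system. Section 23.2 requires unanticipated risks to go promptly to the IRB/IEC. None of these is AE or SAE collection, and a seizure in a population where seizures are called common need not qualify as unanticipated.

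**The case against.** The strongest reply is that the window is deliberate and consistent. Sections 13.2, 18.0 and 23.2 agree, and the flow charts match. A protocol-related AE is first of all an AE, so it can be read as post-dose only. On that reading the examples still have content: the 4-week break after radiotherapy is drug-free, and blood draws, ECGs and MRIs continue after dosing. All of those events are recorded. This reading is possible. It does not close the gap, because an event before dosing that results from the protocol's own instructions still has no place to be reported.

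Other parts of the reply limit the point, and they stand:

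- A reader might infer that the withdrawal is mandatory. Section 12.0 says it should happen, allows such drugs where they cannot be avoided, and is not backed by an eligibility criterion in Sections 11.1 or 11.2. Some patients may also have stopped before consent.
- A reader might infer that a seizure after withdrawal is caused by the study. The documents do not support that. Seizures have a background rate here, and Section 23.1 leaves attribution to the investigator or medical monitor.
- A reader might infer that such patients vanish from the record. They do not: a log entry and a reason remain, and perhaps history and medication entries.
- Screening procedures are mostly low-risk, and standard-of-care results may be used, so the drug withdrawal carries most of the weight.

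**Conclusion.** The gap is real. Between consent and first dose, events that the protocol would call protocol-related are not captured as AEs or SAEs, and an event that leads to screen failure leaves only a log entry and a reason. The uncaptured time is up to 21 days per patient. It includes every on-study pre-dose day of an instructed withdrawal where one takes place. The total is unknown because the share of patients affected is not given, and no figure for it should be quoted.

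It would be wrong to conclude that the trial's main safety results are distorted. The primary safety population in Section 21.3 requires at least one dose, and the on-treatment tables, DLT assessment, recommended Phase 2 dose and PFS do not use pre-dose events. What is missing is an account of possible harm from entering the study. The conclusion rests on reading the recording rules as written, and on at least some patients stopping such a drug, or having a procedure event, after consent. No position is taken on whether or how anticonvulsants should be stopped.

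**What to change.** Reconcile the AE definition, the protocol-related AE definition and the recording rule, so that from signed consent to the first PLX3397 dose sites record and report AEs and SAEs that the investigator or medical monitor judges protocol-related, including in screen failures. From the first dose, recording stays as it is.

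The edits need to match throughout:

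- **Section 23.1:** let a protocol-related event be an AE in a consented patient who has not yet received study drug.
- **Sections 18.0 and 23.2:** state the pre-dose window, and remove the screen-failure exclusion for these events.
- **Sections 13.1 and 13.2:** add the pre-dose event check at Screening and at C1D1 before dosing.
- **Both flow charts:** add the Screening entry in the adverse event row.
- **Section 21.5:** list pre-dose events separately, so that the treatment-emergent tables do not change.

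The cost is amendment wording, one short listing and a few extra SAE forms, some of them for patients who are never dosed.

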### **23.2 Recording and Reporting**

A patient's AE or SAE can occur from the time the patient receives the first dose of study drug up to 28 days after the last dose.

The investigator must follow-up on all drug-related AEs, SAEs, and other reportable information until the events have subsided, returned to baseline, the patient has initiated any other anticancer treatment, or in case of permanent impairment, until the condition stabilizes. Pregnancies and overdoses are not considered AEs but must be reported to the Sponsor.

All AE and SAEs must be recorded on source documents and collected in TEMPO. All AEs and SAEs for patients who are not screen failures will be recorded in the eCRFs.

AEs should be based on the signs or symptoms detected during the physical examination and on clinical evaluation of the patient. In addition to the information obtained from those sources, the patient should be asked the following nonspecific question: "How have you been feeling since your last visit?" Signs and symptoms should be recorded using standard medical terminology.

Any unanticipated risks to the patients must be reported promptly to the IRB/IEC.

